that some participants may know each other, the evaluators believe that the private and personal nature of the intervention coupled with the personalization of messaging received in one-on-one sessions serves to deter the diffusion of MARSSI content from treatment to control participants. However, we do not have data that allow us to assess this issue and recognize it is plausible that treatment may be diffused in some way.

3. Program Implementation Analysis

This section lays out plans for analyzing implementation data for understanding and documenting program implementation.

Table 1. Planned implementation analysis

Research question	Measure	Operationalization	Data sources
Fidelity			
How much of the program was delivered as intended?	Counselor- and observer-reported average percent of required MARSSI activities that are completed, by session and overall	
For each individual session, the proportion of required activities completed will be calculated as the number of required activities that the counselor/observer reports were completed divided by the total number of required activities for that session. There are 13 total activities that can be completed in the main counseling session and 10 total activities that can be completed in the booster session.
 
Activities are counted as having been 'completed' if the counselor/observer reports that the activity has been completed in full.
 
The average percent of required MARSSI activities completed will be calculated for each session type (main counseling or booster session) and overall (combining main counseling and booster session).
	
Counselors complete an electronic MARSSI Main Counseling Session Self-Report Form after delivering a main counseling session and an electronic MARSSI Booster Session Self-Report Form after delivering a booster session.¹²
 
Observers complete an electronic MARSSI Main Counseling Session Observer Form after observing a selected main counseling session and an electronic MARSSI Booster Session Observer Form after observing a selected booster session.¹³

	Percent of MARSSI participants who received their booster	The number of treatment group participants who completed their booster session, divided by the total number of treatment group participants	
 • Counselor Self-Report Form – Booster Session Form

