¹² Note: For the purposes of this study, delivery as intended requires that participants complete all MARSSI program components within six weeks of being enrolled into the study.

¹³ Session observation entails trained MARSSI observers watching recordings of the counselors delivering sessions to participants (virtually). Counselors are asked to record a certain number of each type of session per month, with the goal of recording and observing a minimum of 10% of all main counseling sessions and booster sessions delivered during the study period. Each recording is first viewed by two observers and then data are reconciled so that there is one final Observation Form associated with each video recording. Observers complete Observer Forms within one month after each recording.

Research question	Measure	Operationalization	Data sources
	counseling session during designated two-week window		
Dosage			
How much programming was received by participants?	Percent of participants who completed the main counseling session	Number of treatment participants who are indicated as having received the main counseling session divided by the total number of treatment participants enrolled in the study	Counselors complete an electronic Consent & Enrollment Session Form in which they indicate if they delivered the main counseling session and an electronic One-Month Follow-Up Data Collection Form in which they indicate if they delivered the booster session.
	Percent of participants who completed at least 14 days of app use	Number of treatment participants who have an indicator of at least 14 days of submitting at least one response in the app divided by the total number of treatment participants enrolled in the study ¹⁴	
	Percent of participants who completed the booster session	Number of treatment participants who are indicated as having received the booster session divided by the total number of treatment participants enrolled in the study	

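### The fidelity measure named for a booster within a two-week window is calculated with no timing condition, so its formula is the same as the any-time dosage measure

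*SAP*

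**What the plan says.** Table 1 asks under Fidelity how much of the program was delivered as intended. The second measure for that question has a name that runs across a page break: it begins "Percent of MARSSI participants who received their booster" and ends "counseling session during designated two-week window". Its operationalization cell reads "The number of treatment group participants who completed their booster session, divided by the total number of treatment group participants", and its data source is the "Counselor Self-Report Form – Booster Session Form".

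Under Dosage, which asks how much programming participants received, the booster measure is "Number of treatment participants who are indicated as having received the booster session divided by the total number of treatment participants enrolled in the study". The source for that row is the One-Month Follow-Up Data Collection Form, completed by counselors, "in which they indicate if they delivered the booster session".

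Footnote 12, whose marker sits in the data-source cell of the preceding fidelity row, says that "delivery as intended requires that participants complete all MARSSI program components within six weeks of being enrolled into the study". Section 2 places the booster after four weeks of app use. Later rows of Table 1 refer to the end of a booster delivery window, because a participant feedback form is collected then. The SAP does not state when the two-week window starts or ends.

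**The concern.** The operationalization column is where the SAP fixes how each measure is calculated. In this row the name promises a timing-restricted percentage and the calculation delivers an unrestricted one. The page break does not explain this. Only the measure name continues onto the next page; the operationalization sentence is complete before the break, and its continuation cell is empty.

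Two things follow. First, the row cannot show whether boosters were delivered on schedule, which is what separates it from the dosage row. Second, a reader of the final report who sees the measure's name would take the figure as timely delivery when the formula has counted every completed booster. Because the window is not defined, two analysts who tried to honour the name could also arrive at different figures.

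**Working it through.** The SAP gives no value for this measure, so there is no figure to reproduce. The check compares the definitions term by term.

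**Notation**
- N = treatment group participants. The fidelity row divides by all treatment group participants and the dosage row by all treatment participants enrolled; I read both as the treatment arm.
- B = treatment participants who completed the booster at any time.
- L = those among B whose booster fell outside the designated window.

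**The three quantities**
- Fidelity, as operationalized: B/N.
- Dosage, as operationalized: B/N.
- Fidelity, as named: (B − L)/N.

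**Difference between the written and the named fidelity measure**

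B/N − (B − L)/N = L/N.

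The two written formulas are therefore the same ratio, and the written fidelity formula exceeds the named quantity by the share of the treatment arm whose booster fell outside the window.

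**Size**

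The SAP gives neither B/N nor L. For illustration only, assume B/N = 70% and let the share of completed boosters outside the window (L/B) vary:

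| Assumed L/B | As named, (B − L)/N | As written, B/N | Overstatement, L/N |
|---|---|---|---|
| 0% | 0.70 × 1.00 = 70% | 70% | 0 points |
| 10% | 0.70 × 0.90 = 63% | 70% | 7 points |
| 20% | 0.70 × 0.80 = 56% | 70% | 14 points |
| 30% | 0.70 × 0.70 = 49% | 70% | 21 points |

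The written figure stays at 70% in every row, so it cannot register lateness.

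**Whether footnote 12 supplies the missing condition**

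It shows that timing belongs to the SAP's idea of intended delivery, but it does not define the two-week window. It sets one limit, six weeks from enrollment, for all components together. Combined with the statement that the booster follows four weeks of app use, a reader might infer a window from about week four to week six. The SAP does not say so, and it does not say whether the window is counted from enrollment or from the start of app use. The operationalization sentence does not refer to the footnote.

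**The case against.** The strongest reply is that the restriction is already in the row. The measure and operationalization cells sit side by side, footnote 12 puts a time limit on intended delivery, and an analyst who reads the whole row would probably apply the window. On that view a qualifier was simply not repeated, and nobody chose to count late boosters. This is fair as an account of intent. It does not rescue the formula, which is a complete sentence giving a numerator and a denominator, neither of them limited in time. Nor could the analyst apply the window from this SAP, since its dates are not given.

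Three stronger readings are tempting, and the document does not support them.

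- *That late boosters are in fact being counted as on time.* The SAP does not say that boosters are delivered after the window, and it does not say that they are barred. Its references to the end of a delivery window could mean that delivery stops there. In that case L = 0 and nothing is overstated, although the row then adds nothing to the dosage row beyond a second source form.
- *That the two reported percentages must be equal.* The definitions are the same ratio, but the fidelity row uses the booster self-report form and the dosage row the one-month follow-up form. Differences in form completion could make the reported values differ. What the formulas cannot produce is a difference due to timing.
- *That a wrong figure would distort the reading of the impact results.* Section 3 presents these data as a way to understand and document implementation. The benchmark model in Section 4e has no fidelity term, and the CACE analyses are framed around participation and dosage. Nowhere does the SAP say that this percentage will be used to interpret a null or positive effect.

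**Conclusion.** The point holds as an internal inconsistency: the formula in the fidelity row does not calculate the quantity that the row names, and it repeats the written ratio of the dosage row. The overstatement of in-window delivery is L/N. Its size cannot be taken from the SAP; under the assumed 70% completion rate it runs from 0 to 21 percentage points as the share of boosters outside the window goes from 0% to 30%. The conclusion rests on reading the operationalization cell literally and on both denominators being the treatment arm.

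The importance is low. This is a descriptive implementation measure, and no primary or secondary impact estimate depends on it. It is worth correcting because the edit is small and the row otherwise does not answer the fidelity question it sits under.

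**What to change.** In Table 1, Fidelity, restrict the numerator to treatment participants whose booster session date falls inside the designated two-week window, and keep the denominator. State how the window is defined, including its reference date and its start and end as the study actually applied them, and reconcile that definition with the six-week limit in footnote 12. Leave any-time completion to the dosage row, so that the two rows measure different things.

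The cost is a phrase in the operationalization cell, one sentence defining the window, and a date comparison at analysis. This assumes that the session date is recorded on the booster form or another study record, which the SAP does not state.

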To be eligible for enrollment, individuals must meet all of the following criteria: 1) biologically able to become pregnant; 2) 16-21 years of age;⁵ 3) fluent in English; 4) own a smartphone; 5) have the technical capacity to participate; 6) not currently pregnant; 7) not trying to become pregnant; 8) not have given birth during the six months preceding eligibility screening; 9) not be married or engaged to be married at the time of eligibility screening; 10) report having penile- vaginal sex in the past 3 months; 11) report having penile-vaginal sex at least once a week, on average; 12) score at least 8 on the PHQ-8 depression screening tool;⁶ 13) self-report visiting a reproductive health provider in the past two years;⁷ 14) report having done at least one of the following during the 3 months preceding eligibility screening: a) not used a condom every time they had sexual intercourse; b) used condoms, a diaphragm, cervical cap, spermicide, sponge, fertility awareness, or withdrawal as a primary form of birth control; c) had sexual intercourse with more than one person; d) had sexual intercourse within two hours after using drugs or alcohol; or e) been treated for a sexually transmitted infection/disease; 15) consent to participate in the study; and 16) not identified as fraudulent.⁸

The intent-to-treat sample (ITT) is comprised of eligible individuals who are enrolled into the study during the enrollment period (June 2021 to April 2023).

a. Random assignment process

- i. **Unit of randomization:** Random assignment occurs at the individual participant level.
- ii. **Random assignment procedure:** The Policy & Research Group (PRG) is responsible for all aspects of random assignment. Random assignment blocks of varying sizes assign participants to treatment or control condition at an equal (i.e., 1:1) assignment ratio. PRG produced this allocation list with an existing algorithm available in Stata (random allocation command, *ralloc*) and did so separately for each of the potential 255 study coordinator-state combinations.⁹ The allocation lists were produced by a PRG senior research analyst and stored on a secure server.

Electronic random assignment is conducted just prior to the administration of the online baseline questionnaire and is carried out by the study coordinators. Study coordinators were each given a sequential list of unique study IDs for every U.S. state. They assign a number (based on the state where the individual would seek

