participants are either coded as currently using effective non-barrier contraception or not currently using effective non-barrier contraception. Data used to assess the impact of the treatment (MARSSI) on contraceptive use are obtained from the following item on the *Participant Questionnaire*, which is administered to both the treatment and control groups at baseline, short-term follow-up (three months post-intervention period), and long-term follow-up (six months post-intervention period).

- Please indicate which method of prescription birth control you are currently using.
 - Oral contraceptives (for example, the pill)
 - The patch (for example, Ortho Evra)
 - The shot/injection (for example, Depo-Provera)
 - The ring (for example, NuvaRing)
 - The implant (for example, Implanon or Nexplanon)
 - IUD (for example, ParaGard, Skyla, Mirena, Kyleena, Liletta)
 - None of the above

Persons who indicate that they are currently using any of the listed methods are considered to be currently using effective non-barrier contraception and are coded as 1. Persons who select *None* are considered to not be currently using effective non-barrier contraception and are coded as 0.

MARSSI will be considered to have a positive impact on non-barrier contraceptive use if, as compared to participants who are assigned to the control group, a larger proportion of participants who are offered MARSSI report using effective non-barrier contraception at the three-month post-intervention period and the difference between groups is statically significant.

Number of sexual partners

Number of sexual partners is constructed as a count variable – the number of sexual partners the participant reports that they have had in the past three months.²⁵ Data used to assess the impact of the treatment (MARSSI) on number of sexual partners are obtained from the following item on the *Participant Questionnaire*, which is administered to both the treatment and control groups at baseline, short-term follow-up (three months post-intervention period), and long-term follow-up (six months post-intervention period).

- How many sexual partners have you had in the past 3 months?

Persons who indicate that they have not had any sexual partners in the past three months are coded as having zero sexual partners.

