Frequency of using dual contraception during vaginal sex in the past 30 days	Participant Questionnaire	
The measure is operationalized as the number of times in the past 30 days a person reports using dual contraception during vaginal sex.
 
The measure is calculated from the following item:
 
 • In the past 30 days, how many times did you have vaginal sex using both a condom and one of the list forms of prescription birth control at the same time? 
The resulting variable is continuous with values that range from 0 to k, where 0 indicates that a person has not used dual contraception during vaginal sex in the past 30 days, and k indicates the number of times the person has used dual contraception in the past 30 days. Persons who indicate that they have not had vaginal sex in the past 30 days are excluded from this analysis.
	Three months post-intervention (four months post-baseline) and six months post-intervention (seven months post-baseline)
Use of effective non-barrier contraception during last vaginal sex	Participant Questionnaire	
The measure is operationalized as a dichotomous variable indicating if someone used effective non-barrier contraception or not during last vaginal sex.
 
The measure is calculated from the following item:
 
 • Considering the LAST time you had vaginal sex, which of the following did you use? 
 ○ Oral contraceptives (for example, the pill) ○ The patch (for example, Ortho Evra) ○ The shot/injection (for example, Depo-Provera) ○ The ring (for example, NuvaRing) ○ Implant (for example, Implanon or Nexplanon) 	Three months post-intervention (four months post-baseline) and six months post-intervention (seven months post-baseline)

		
  IUD (for example, ParaGard, Skyla, Mirena, Kyleena, Liletta)  Emergency contraception (ella, Plan B)  Condoms  The sponge  Diaphragm  Foam or spermicide  Natural family planning (rhythm method)  I did not use any of these 	
		
A person who selects Oral contraceptives, The patch, The shot/injection, The ring, Implant, or IUD is given a value of 1 for the measure. A person who selects anything else is given a value of 0 for the measure.
	

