Use of condoms during last vaginal sex	Participant Questionnaire	
The measure is operationalized as a dichotomous variable indicating if someone used condoms or not during last vaginal sex.
 
The measure is calculated from the following item:
 
 • Considering the LAST time you had vaginal sex, which of the following did you use? 
  Oral contraceptives (for example, the pill)  The patch (for example, Ortho Evra)  The shot/injection (for example, Depo-Provera)  The ring (for example, NuvaRing)  Implant (for example, Implanon or Nexplanon)  IUD (for example, ParaGard, Skyla, Mirena, Kyleena, Liletta)  Emergency contraception (ella, Plan B)  Condoms  The sponge  Diaphragm  Foam or spermicide  Natural family planning (rhythm method)  I did not use any of these 
A person who selects Condoms is given a value of 1 for the measure. A person who selects anything else is given a value of 0 for the measure.
	Three months post-intervention (four months post-baseline) and six months post-intervention (seven months post-baseline)
No effective contraception used during last vaginal sex	Participant Questionnaire	
The measure is operationalized as a dichotomous variable indicating if someone did not use effective contraception during last vaginal sex.
 
The measure is calculated from the following item:
 
 • Considering the LAST time you had vaginal sex, which of the following did you use? 
  Oral contraceptives (for example, the pill)  The patch (for example, Ortho Evra)  The shot/injection (for example, Depo-Provera)  The ring (for example, NuvaRing) 	Three months post-intervention (four months post-baseline) and six months post-intervention (seven months post-baseline)

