		
  Implant (for example, Implanon or Nexplanon)  IUD (for example, ParaGard, Skyla, Mirena, Kyleena, Liletta)  Emergency contraception (ella, Plan B)  Condoms  The sponge  Diaphragm  Foam or spermicide  Natural family planning (rhythm method)  I did not use any of these 	
		
A person who selects I did not use any of these is given a value of 1 for the measure. A person who selects anything else is given a value of 0 for the measure.
	
Use of dual contraception during last vaginal sex	Participant Questionnaire	
The measure is operationalized as a dichotomous variable indicating if someone used both effective non-barrier contraception AND condoms or not during last vaginal sex.
 
The measure is calculated from the following item:
 
 • Considering the LAST time you had vaginal sex, which of the following did you use? 
  Oral contraceptives (for example, the pill)  The patch (for example, Ortho Evra)  The shot/injection (for example, Depo-Provera)  The ring (for example, NuvaRing)  Implant (for example, Implanon or Nexplanon)  IUD (for example, ParaGard, Skyla, Mirena, Kyleena, Liletta)  Emergency contraception (ella, Plan B)  Condoms  The sponge  Diaphragm  Foam or spermicide  Natural family planning (rhythm method)  I did not use any of these 	Three months post-intervention (four months post-baseline) and six months post-intervention (seven months post-baseline)
Frequency of having oral sex in the past 30 days	Participant Questionnaire	
The measure is operationalized as the number of times in the past 30 days a person reports having oral sex.
 
The measure is calculated from the following item:
 
 • In the past 30 days, how many times have you had oral sex? 	Three months post-intervention (four months post-baseline) and six months post-intervention

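### Secondary outcome 2k/3h is named for no effective contraception but coded as no listed method used, so rhythm-only and emergency-contraception-only users count as protected

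*SAP*

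**What the plan says.** SAP section 1.b lists this outcome twice among the secondary questions, as 2k at three months and 3h at six months. Table 3 (section 4.b) describes it: "The measure is operationalized as a dichotomous variable indicating if someone did not use effective contraception during last vaginal sex". The source is q19 in Appendix A, a select-all item with 13 options: six prescription methods, emergency contraception, condoms, sponge, diaphragm, foam or spermicide, natural family planning, and a none-of-these option. Under the coding rule, a person who ticks the none-of-these option "is given a value of 1 for the measure. A person who selects anything else is given a value of 0 for the measure".

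Three other places bear on what the SAP means by effective:

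- **Table 3, outcome 2i/3f (effective non-barrier method at last vaginal sex), also from q19.** The six prescription methods score 1. For all other answers, "A person who selects anything else is given a value of 0 for the measure".
- **Section 4.b, primary outcome 2.** The item lists the same six methods, and participants "currently using any of the listed methods are considered to be currently using effective non-barrier contraception and are coded as 1".
- **Section 2, eligibility criterion 14(b).** One of the qualifying behaviours is having "used condoms, a diaphragm, cervical cap, spermicide, sponge, fertility awareness, or withdrawal as a primary form of birth control".

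The SAP nowhere defines effective contraception without the non-barrier qualifier.

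**The concern.** The name and the rule describe different things. The name promises the proportion left without effective contraception at last sex. The rule delivers the proportion who used nothing on the list. Someone who relied only on the rhythm method is coded the same as someone with an IUD.

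Two consequences follow. The reported proportion without effective contraception would be too low. And a participant who moves from a weaker method to a prescription method stays at 0 on this variable, so it cannot register that change. The outcome would still be reported under a label that leads readers to think it could.

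**Working it through.** No sample size, power or significance figure is involved, and the SAP gives no method-mix figures. The check applies the Table 3 rules to each q19 option taken as the only answer, then writes the error algebraically.

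**Step 1. Sole-answer profiles.**

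| Only q19 answer | Options | 2i/3f effective non-barrier | 2j/3g condom | 2k/3h no effective contraception |
|---|---|---|---|---|
| Pill, patch, injection, ring, implant, IUD | 6 | 1 | 0 | 0 |
| Condoms | 1 | 0 | 1 | 0 |
| Emergency contraception, natural family planning | 2 | 0 | 0 | 0 |
| Sponge, diaphragm, foam or spermicide | 3 | 0 | 0 | 0 |
| None of these | 1 | 0 | 0 | 1 |

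The options sum to 6 + 1 + 2 + 3 + 1 = 13. Five of the 13 profiles score 0 on all three measures.

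**Step 2. Which of the five are contradictory.**

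- *Rhythm and emergency contraception.* Neither is a barrier method. By the 2i/3f rule their sole users did not use an effective non-barrier method, and by their own answers they used no condom or other barrier. No class of effective method is left for them, yet 2k/3h codes them as not lacking one. The SAP's own rules conflict.
- *Sponge, diaphragm, foam or spermicide.* Sponge and diaphragm are barrier methods, so 0 on effective non-barrier and 0 on condoms does not by itself make 0 on 2k/3h wrong. For these two and for foam or spermicide, the SAP simply does not say whether they count as effective. Criterion 14(b) does not settle it, because condoms are in the same list.

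**Step 3. Size of the error.** Suppose effective means the six prescription methods plus condoms. For each respondent let:

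- C = the outcome as now coded;
- W = 1 if the person selected one or more of the other five methods but no prescription method and no condom, otherwise 0;
- R = the recoded outcome.

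C and W cannot both be 1, so R = C + W. It follows that:

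- prevalence: P(R = 1) = P(C = 1) + w, where w is the share with W = 1, so the present coding understates prevalence by exactly w;
- unadjusted treatment difference: Δ(R) = Δ(C) + Δ(w), so the present coding omits the difference between arms in w.

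A move from rhythm only to the pill is 1 to 0 on R and 0 to 0 on C. A move from no method to rhythm only is 1 to 1 on R and 1 to 0 on C. If sponge, diaphragm and foam or spermicide were declared effective, the algebra would be the same, with W confined to users of rhythm or emergency contraception who selected no effective method.

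**Step 4. Reach.** Section 1.b lists 7 + 17 + 16 = 40 full-sample secondary outcomes, and this one accounts for 2 of them. It also carries into the subgroup and CACE questions. Under section 4.f the secondary models follow the benchmark approach, which adjusts for the baseline measure of the outcome, so the same coding would also enter as a covariate.

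**The case against.** The strongest reply is that little depends on this variable. The rule is explicit, reproducible and identical in both arms. Section 1.b (footnote 3) says secondary outcomes are not critical to judging efficacy, and the introduction says secondary findings may or may not be reported. A shift to prescription methods is recorded on 2i/3f from the same item and should appear on primary outcome 2. The recoded version is also nearly redundant: among the same respondents, P(R = 1) = 1 − P(2i) − P(2j) + P(2l), where 2l is dual use, and all three are already planned at both times. All of this stands and limits the importance of the point. It does not make the label correct.

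The documents do not support several stronger readings that a reader might infer:

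- *All five weaker methods are miscoded by the SAP's own standard.* This is shown only for rhythm and emergency contraception. For the other three, a definition is missing.
- *Criterion 14(b) shows the SAP regards these methods as ineffective.* It lists condoms too, so the same argument would disqualify condoms.
- *Withdrawal users are misclassified.* Withdrawal is not a q19 option, so a withdrawal-only user would be left with the none-of-these option and score 1. The recode also gives 1.
- *The understatement is some particular number of points.* The SAP has no method mix. Any range for w, such as 5 to 15%, would be an assumption handed back as a result.
- *The trial would miss a move to prescription methods.* Only this variable would.

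**Conclusion.** The point holds in a limited form. As written, 2k/3h measures whether no listed method was used. For rhythm-only and emergency-contraception-only users this contradicts the sister measure built from the same item. For sponge, diaphragm and foam or spermicide, the SAP leaves the meaning of effective undefined.

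Prevalence of no effective contraception is understated by w, and the unadjusted effect omits the between-arm difference in w. Neither can be computed from the SAP. Criterion 14(b) admits people who rely mainly on some of these methods, so w is unlikely to be zero. The conclusion rests on the coding rules alone, apart from Step 3, which takes prescription methods plus condoms as the effective set. The SAP implies that set through 2i/3f and 2j/3g but does not state it.

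The primary outcomes, analytic samples and tests are untouched. The change is worth making because the rule gives a wrong value for a named outcome and is cheap to correct.

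**What to change.** Either of two edits to Table 3 resolves it.

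1. State which q19 methods count as effective for this outcome, and code 1 when none of them is selected and 0 otherwise. For consistency with 2i/3f and 2j/3g, that would mean 1 when none of the six prescription methods and no condom is selected. Apply the rule at baseline as well as at both follow-ups, so that the baseline covariate matches the outcome.
2. Keep the present coding, rename the outcome *No listed method used at last vaginal sex* here and in section 1.b, and do not interpret it as effective contraception.

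The first keeps the intended meaning, and the second is sufficient if the developers meant any listed method. The item is already collected as select-all, so either option costs a short text edit and at most one line of code, with no new data.
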